4. HYPOTHESES

For each specified research question, state the hypothesized result(s) and briefly describe why these results are anticipated.

Research Question	Hypothesized Result
I1	Primary workshops, support services, and case management services were offered to all participants as needed, with fidelity to the program model.
12	Participants received primary workshop hours (dosage) as intended, with 90% of enrollees receiving at least 90% of primary hours.
R1	Participants will experience better co-parenting relationships outcomes after program participation.
R2	Participants will experience better parenting relationships outcomes after program participation.
R3	Participants will experience better economic stability outcomes after program participation.

^{*} you may add rows by hitting the tab button, or right click and select insert row below

5. RESEARCH DESIGN

For each research question, briefly describe why the research design proposed will answer each research question(s). State whether the proposed evaluation is a descriptive or impact evaluation and justify why the proposed research design is best suited to answer the research question(s).

Research Question	Design	Justification
I1	Assessment of fidelity to program model by tracking programmatic activities on nFORM.	Ensuring full program implementation to ensure that the intervention that is being measured is actually being delivered.
12	Assessment of dosage by measuring the number of primary workshop hours received and exploration of	Ensuring sufficient dosage is being delivered to adequate number of participants and exploring what characteristics are associated with greater workshop participation.

	variation by workshop and participant characteristics	
R1	Pre to post outcome assessment of program participation for improved co-parenting relationships	Significant improvement in co-parenting relationship outcomes from pre to post estimates the maximum amount of benefit that can be attributed to Seedco services in the absence of a counterfactual.
R2	Pre to post outcome assessment of program participation for improved parenting relationships.	Significant improvement in parenting relationship outcomes from pre to post estimates the maximum amount of benefit that can be attributed to Seedco services in the absence of a counterfactual.
R3	Pre to post outcome assessment of program participation for improved economic stability.	Significant improvement in economic stability outcomes from pre to post estimates the maximum amount of benefit that can be attributed to Seedco services in the absence of a counterfactual.

^{*} you may add rows by hitting the tab button, or right click and select insert row below

6. ONGOING GRANTEE AND LOCAL EVALUATOR COORDINATION

Describe how the grantee and local evaluator collaboratively worked together to identify the research question(s) and research design to ensure its feasibility and relevance. Describe how the grantee and local evaluator will continue to work together throughout the evaluation to proactively address unforeseen challenges as they arise and ensure the rigor and relevance of the evaluation and its findings. Describe how the grantee and local evaluator will coordinate dissemination efforts. Describe how these processes will occur while maintaining the independence of the evaluation.

Seedco and the local evaluator, Midwest Evaluation and Research (MER) began the process of collaboration prior to the release of the Funding Opportunity Announcement (FOA) for this project. This included multiple working meetings to discuss the project and the goals that Seedco had for the project, with a specific emphasis on what they had learned as a funded OFA grantee over the last two cohort cycles and what they would like to do differently. This included a discussion of enhancements to the program they believed would enhance participant outcomes, and the resource requirements of these enhancements. Several viable and relevant research question options were developed prior to the FOA and when the FOA was released the team had additional meetings to discuss the program that would be proposed to meet the goals and objectives of Seedco and OFA and how well the research question alternatives developed in advance worked with this program outline. Using this extended collaborative process, the research questions were designed that were most relevant and feasible.

The basis for ongoing coordination between Seedco and MER (the local evaluator) is regular communication, by way of recurring meetings and daily interactions with embedded staff.

Throughout the original proposal process, and during the evaluation planning phase, MER worked in consort with Seedco to design a study with research questions that are appropriate to the intervention. MER guides the process, given our experience designing and running evaluations, and Seedco provides expertise on their community, target population, and program/curricula specifics.

Recurring meetings will include a bi-weekly project CQI team meeting. Under the leadership of the Data Manager and Lead MER Evaluator, the CQI team reviews data from the nFORM and local evaluation systems to identify and mitigate implementation or data issues, and closely examine trends and accomplishments. This team includes Seedco organizational and project leadership, the MER Evaluation team, and front-line staff representatives (e.g., Facilitators, Case Managers).

In addition to CQI team meetings, overall project team meetings occur monthly (at a minimum), with project leaders across MER and Seedco in attendance, to ensure the partnership remains strong and that coordination across organizations is on track. This recurring, ongoing meeting structure is conducive to close coordination, ensuring that challenges can be quickly addressed, and promising strategies can be efficiently maximized.

One of the key components of this coordination effort is the Data Manager, employed with Seedco. The Data Manager functions to bridge the gap between organizations. They will interact with Seedco staff daily while completing their job duties and play a leadership role in the recurring meetings outlined above. See Section 8 below for more details about this role and others. Both the meetings and the roles outlined above will continue throughout the entire project period, providing opportunities to ensure the rigor and relevance of the evaluation and its findings, and to discuss and coordinate dissemination efforts (which will also be shared across MER and Seedco).

MER has experience operating prior evaluations using this described process. Clearly outlining roles and responsibilities maintains the independence of the evaluation. That is, the evaluation team helps identify and illuminate areas of concern or improvement (for the program and the evaluation), but the program staff have responsibility for implementing improvements and providing direct services to participants. In this way, Seedco and MER acknowledge our shared interest in and responsibility for a well-executed project and evaluation, but that MER is also an independent and external organization with a high level of integrity and is not responsible for nor invested in the specific outcomes of the program. This allows for close coordination without allowing for codependence, or for personal interests to influence evaluation findings.

8. SAMPLE

8.1. TARGET POPULATION(S)

For each target population identified in Section 1.2, please describe the target population(s), and explicitly state whether the population(s) differs from those who will be broadly served by the grant. Describe how the target population will be identified. Explicitly state the unit of analysis (e.g., non-residential father, unmarried couple).

Description of Target Population	How is the population different from those who will be broadly served by the grant?	How will the target population be identified?	Unit of Analysis
Low-income, minority, young fathers (and father figures) in the Greater Memphis area	No difference, all program participants will be eligible to be study participants	The sample will be identified and recruited by the program staff. The project has identified multiple referral sources including: HopeWorks A Step Ahead Foundation	Father

St. Andrew AME Church Neighborhood Christian Center Families Matter The RISE Foundation Children & Family Services Maximus Equus Shelby County Community Services Agency Tennessee Voices for Children The Excel Center Church Health Center Christ Community Health Center Cocaine Alcohol Awareness Program Synergy Dorothy Day House

8.2. METHODS TO PROMOTE SUFFICIENT PROGRAM PARTICIPATION

Please describe methods to promote sufficient program participation in the table below.

What methods will you use to Seedco will work with local referral partners and other CBOs ensure sufficient sample is to ensure that there are sufficient sample sizes, The CQI recruited, enrolls, and process will address issues regarding program recruitment participates in the program? and enrollment to ensure targets are met. Who will be responsible for The evaluation sample will not differ from the program recruiting the evaluation population, in that all participants will be invited to sample? participate in the evaluation. Enrollment into the evaluation will be conducted by the Data Manager who will conduct the informed consent process and proctor the baseline data collection efforts.

Please describe any incentives to be offered for program participation and/or completion and/or data collection and/or participation in the evaluation.

Evaluation Participation—No incentives will be used for the two data collections at baseline and post-test while participants are beginning or still engaged in service.

9. DATA COLLECTION

9.1. CONSTRUCTS AND MEASURES

Clearly articulate the constructs of interest, measures to evaluate those constructs, and specific data collection instruments. Provide any information on the reliability and validity of the data collection instruments. For standardized instruments, you may provide the citation for the instrument.

^{*} you may add rows by hitting the tab button, or right click and select insert row below

Construct	Measure	Instrument	Reliability and Validity (if standardized instrument, you provide a citation for the instrument)
Program fidelity	Percent of enrolled participants who received each of the following: 1) primary workshops, 2) employment supports, 3) substantive service contacts, 4) referrals Number of substantive service contacts and referrals per participant	nFORM MIS	
Dosage	Number of primary workshop hours received, percent of target hours received Subgroup exploratory analysis of how dosage varies by workshop and participant characteristics	nFORM MIS	

Co-parenting Relationships	Composite measure that takes the average of 5 survey items related to positive co-parenting interactions with the mother of participant's youngest child (continuous, scale from 1-5 where 1 is strongly disagree and 5 is strongly agree). Improvement will be measured by a participant's change score, calculated by subtracting their pre-program composite score from their post-program composite score.	nFORM Community-Based Fathers Survey (A13: d-h)	Reliability and validity will be assessed with a correlation matrix and factor analysis
Parenting Relationships	Daily hours spent with youngest child in past 30 days (change score from preprogram to post-program) Frequency of reaching out to youngest child in past 30 days (change score from preprogram to post-program) Composite measure that takes the average of 10-11 survey items related to positive parenting behaviors with youngest child (continuous, scale from 1-5 where 1 is Never, 2 is 1 to 2 days per month, 3 is 3 or 4 days per month, 4 is 2 or 3 days per week, and 5 is every day or almost every day). Improvement will be measured by a participant's change score, calculated by subtracting their pre-program composite score from their post-program composite score.	nFORM Community-Based Fathers Survey (A2b, A2c, A5a-d: a-k)	Reliability and validity will be assessed with a correlation matrix and factor analysis
Economic Stability	Difficulty paying bills (categorical, scale from 1 to 4 where 1 is never and 4 is very often). Improvement will be measured by change score in participant's reported difficulty, calculated by subtracting their	nFORM Community-Based Fathers Survey B4, B3, B3a.	N/A (individual items will not be combined)

post-program value from their pre-program value.	
Has savings account at end of program, among those who came into the program with no savings account	
Has checking account at end of program, among those who came into the program with no checking account	

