1. PROGRAM SUMMARY

Please provide a brief summary of your grant project including the needs to be addressed, the services provided, and the population served.

The Strong Fathers, Stronger Families-Midsouth (SFSF-Midsouth) FIRE Project conducted by the Structured Employment Economic Development Corporation (Seedco) builds upon Seedco's regional capacity and track record accumulated since 2004 and adapts ten years of experience operating an ACF-funded Responsible Fatherhood Program in New York City to meet the needs of fathers in the Memphis, TN metropolitan region.

Sustained long term employment of parents is one of the key driving factors affecting child well-being. Fatherhood programs may not have the lasting effects program planners and policy makers expect to see, as participants who have successfully completed a program and started a job often do not maintain employment. This inability to sustain employment has a ripple effect across other components of fatherhood, including parenting or partnership relationships.

Needs: Seedco's targeted geographic community for the proposed SFSF-Midsouth program is Shelby County and Tipton County in Tennessee and Crittenden County in Arkansas (the Greater Memphis Metropolitan region). This region is distinguished by high rates of poverty, concentrations of African American populations, and a largely urban center surrounding the Greater Memphis Metropolitan area. These communities are among the poorest in the region, with resources and opportunities further constrained by racial disparity. Participants served via this funding face a challenging economic climate and many face societal and emotional barriers. Seedco's needs analysis confirmed what the agency already knows from its experience serving many fathers, families, and local residents— that these individuals grapple with poverty, incarceration, crime, and single parenthood, or family instability. In short, this region needs and deserves a quality HMRF program.

Services: The SFSF-Midsouth Program will provide economic stability, healthy relationship, and parenting/fatherhood education via evidence-based curricula in combination with intensive case management to participants based on the results of a needs assessment completed at program enrollment.

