1. RESEARCH QUESTIONS

1.1. OVERVIEW OF RESEARCH QUESTIONS

The primary overall research questions for this descriptive evaluation, which will be assessed utilizing pre- and post-surveys from nFORM, focus on program services and seeks to understand, "Is Strong Fathers, Stronger Families program participation associated with better participant outcomes?" This overall line of inquiry is operationalized by focusing on specific short-term outcomes to determine if parenting, co-parenting, and economic stability outcomes are improved after program participation.

No	Research Question	Implementation or Outcome?
11	Are participants offered primary workshops and support services as intended (fidelity)?	Implementation
12	How many primary workshops do participants attend (dosage), and how does this vary by workshop characteristics (e.g., timing and length of sessions) and participant characteristics (e.g., age, employment status, relationship status)?	Implementation
R1	Do SFSF-Midsouth participants experience significant increases in Co-parenting Relationship outcomes after program participation?	Primary Outcome
R2	Do SFSF-Midsouth participants experience significant increases in Parenting Relationship outcomes after program participation?	Primary Outcome
R3	Do SFSF-Midsouth participants experience significant increases in economic stability outcomes after program participation?	Primary Outcome

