3. LOGIC MODEL

Clearly demonstrate how the research question(s) (and the related implementation features and/or participant outcomes) link to the proposed logic model and the theory of change for the program. You may append a copy of your logic model to this document.

See Appendix A for Theory of Change Logic Model

The appended logic model specifies a theory of change for delivering fatherhood curriculum and postemployment services to SFSF participants. Service delivery processes specified in the model are linked to the desired outcome. Model specification incorporates a descriptive study design to determine if participants report significantly improved primary outcomes after program participation.

Service delivery processes: Key aspects of service delivery processes in the theory of change—goals, inputs, activities, and outputs—articulate the experiences that are designed to solve specific problems for those who agree to participate in the SFSF Program. Solving each problem identifies three broad service delivery goals to maximize participation benefits for study groups as explained below:

- Goal 1 Deliver primary workshop hours and support services: Program participants will receive the Blueprint and 24/7 Dad curricula, in combination with employment support services and case management through Seedco, but only after receiving an orientation about the SFSF and giving project staff informed consent to participate in study activities.
- Goal 2 Conduct Continuous Quality Improvement (CQI) to ensure full implementation of program: Reports prepared and presented to the CQI Team by evaluators will use a series of performance indicators to track key outputs over time to identify any primary or support SFSF services delivered to program participants that might fall short of the intended amounts to be offered (i.e., fidelity standards) and received (i.e., dosage thresholds) by them. The CQI Team will then work with project staff to develop and implement performance interventions to address any outputs that need improvement to ensure the services offered to and received by participants meet the intended amounts by the end of each program year.
- Desired Outcomes: Outcomes specified in the logic model theorize the primary outcomes that are
 desired for program participants after they receive primary workshop hours, case management support
 services, and employment support services.

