Missing data for the implementation outcomes could happen as a result of programmatic data entry issues. For the sake of this evaluation, we assume that any primary or support services received by a participant are being accurately logged into nFORM, so a lack of documented attendance, service contacts, referrals, etc. is indicative of lack of services (i.e., a participant not receiving the program components as intended).

...

Assessing non-response bias

We will conduct response rate analysis for each primary outcome of interest to assess non-response bias and adjust for threats to internal validity. Using data from the Applicant Characteristics Survey, we will look at demographics (race, ethnicity, age, education level) and primary reason for joining the program among participants who fall into each of the following categories: 1) non-respondents who answered no surveys after the ACS, 2) respondents who completed the pre-survey only, 3) respondents who completed the post-survey only, and 4) respondents who completed both the pre-and post-survey (complete case).

Analytic approach

The main goal of this descriptive study is to assess pre-post change scores in the outcomes listed above among program participants before and after primary workshops. We will use paired sample t-tests to assess the magnitude and significance of changes among program participants in the analytic sample for each outcome. For binary economic stability outcomes, we will descriptively report the percent of participants who opened a checking or savings account during the course of the

program. We will adjust our p-values for multiple hypothesis testing and report the adjusted p-values in the appendix of the final report.

For the implementation analysis, program fidelity will be descriptively reported by the percentage of enrolled participants who receive: 1) any primary workshops, 2) employment supports, 3) substantive service contacts, 4) referrals. The program aims to provide all participants each of these four program components, so the percentage of participants who receive each of these will be compared to the 100% benchmark. Number of substantive service contacts per participant will also be compared to the benchmark of 8 SSCs set by OFA for FIRE grantees.

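### Fidelity (I1) is defined by what was offered but measured by what fathers received against a 100% benchmark, so the figure cannot separate non-delivery from non-uptake or lack of need

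*Protocol*

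**What the plan says.** **What I1 is about.** Protocol section 1.1 frames the question in terms of offering: "Are participants offered primary workshops and support services as intended (fidelity". The I1 hypothesis (Protocol section 4) adds a condition on need: "Primary workshops, support services, and case management services were offered to all participants as needed, with fidelity to the program model". Under Goal 2 of the logic model (Protocol section 3), the quality-improvement reports are to look for services falling short of "the intended amounts to be offered (i.e., fidelity standards) and received (i.e., dosage thresholds) by them". So the plan has its own split, with fidelity on the offering side and dosage on the receiving side.

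**How it is measured.** The Program fidelity row of Protocol section 9.1 gives "Percent of enrolled participants who received each of the following": primary workshops, employment supports, substantive service contacts and referrals. It adds counts of contacts and referrals per participant. The SAP (section 1, Analytic approach) repeats the receipt measure, specifies the workshop item as any primary workshops, and states that "the percentage of participants who receive each of these will be compared to the 100% benchmark". Its reason is that the program means to give every participant all four components. Contacts per participant are also compared with a benchmark of 8. For the implementation outcomes, the SAP treats anything undocumented as a service not received.

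**Need.** The Program Summary says services are provided "to participants based on the results of a needs assessment completed at program enrollment".

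**Workshop amount.** Protocol section 1.2 gives the primary workshop curricula as 40 hours (R1 and R2 rows). Hours received and percent of target hours are measured under dosage (I2), with a 90% benchmark in the SAP.

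**The concern.** By the plan's own definition, the fidelity measure is a dosage or uptake measure. Protocol section 5 justifies I1 as a check that the intervention being evaluated is really being delivered. A percentage of fathers who received something depends on delivery, but also on whether fathers took up what was offered and whether they needed it. If the figure falls short of 100%, the report cannot say which of these was the cause, and the remedies differ: schedule the missing sessions, work on retention, or do nothing.

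For workshops there is a second gap. Any attendance counts in full, so the item says nothing about how much of the curriculum was held. At stake is the interpretation of I1 and, through it, the description of the program that the outcome results refer to. The outcome analyses themselves are not touched.

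**Working it through.** **1. The plan's own figure.** The documents state no sample size or test for I1. The figure that bears on it is the target table in the Program Summary.

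- Enrolled: 175 + 4 × 350 = 1,575.
- At least one primary workshop: 175 + 4 × 350 = 1,575, so 1,575/1,575 = 100%. This agrees with the SAP benchmark for the workshop item.
- At least 90% of workshops: 158 + 4 × 315 = 1,418, or 90.0% of enrolled.
- All workshops: 118 + 4 × 236 = 1,062, or 67.4% of enrolled.

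The totals reproduce. The workshop item under fidelity corresponds to the first and least demanding attendance target.

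**2. What a percent-received figure contains.** For a service given on need,

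share received = share in need × share of those offered it × uptake among those offered.

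The documents give none of the three factors, so these values are assumptions:

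| In need | Offered, if in need | Uptake | Received |
|---|---|---|---|
| 80% | 100% | 90% | 72% |
| 100% | 72% | 100% | 72% |
| 60% | 100% | 90% | 54% |
| 95% | 100% | 100% | 95% |

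The first two rows give the same reported figure. In the first, every father in need was offered the service; in the second, 28% were not. With offering held at 100%, need of 60–95% and uptake of 90–100% give 54–95% received, always below the benchmark.

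**3. Universal need.** Suppose, as the SAP's reason for 100% implies, that everyone should get each component. With everyone offered it and 99% uptake, the expected shortfall is 1,575 × 0.01 = 15.75, about 16 fathers. If fathers act independently, the probability that all 1,575 receive it is 0.99^1575 ≈ 1.3 × 10⁻⁷; at 99.9% uptake it is 0.999^1575 ≈ 0.21. Some shortfall from 100% is then to be expected even with complete offering.

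**4. The workshop item.** Session length is not given. Assuming 1 to 4 hours, one session is 1/40 to 4/40, or 2.5% to 10% of the curriculum, and a father who attended one counts in full.

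**5. Whether I2 fills the gap.** Take fathers who each received 20 of 40 hours, with the target fixed at 40:

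- 40 hours held, 20 attended: fidelity item 100%, dosage 20/40 = 50%.
- 20 hours held, all attended: fidelity item 100%, dosage 20/40 = 50%.

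I2 detects the low amount in both cases. Neither measure tells the cases apart; hours held (40 against 20) would.

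**6. The passages on who should receive what.** The hypothesis in Protocol section 4 conditions on need, and the Program Summary ties services to a needs assessment. The SAP's 100% benchmark rests on all participants receiving all four components. Both cannot define full fidelity for employment supports and referrals unless every father is taken to need them, which the documents do not say.

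**The case against.** The strongest reply is that the implementation analysis is read as a whole. A reader might infer that a program delivering one session would satisfy I1. The documents do not support that: the lenient wording attaches only to workshops, the other three components are each compared with 100%, and contacts are also set against 8. A program that held one session and did nothing else would score 0% on three components and 0 contacts.

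A reader might also infer that a curriculum cut short would go unnoticed. That is not so either. I2 measures hours received against a 90% benchmark and would show the shortfall, though not its cause.

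Three further points are fair. The question says services are offered as intended; the reference to need is in the hypothesis, and the SAP states a reason for its benchmark. The comparison is descriptive, with no pass/fail rule, so no formal wrong verdict on the program follows. And 1,575 of 1,575 is a target, not a result, so it does not show that the workshop item will be at its ceiling.

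What remains after all this is the mismatch between offering and receiving, which neither I2 nor the benchmark of 8 resolves, and the conflict between need and universal provision. Recorded receipt is a defensible proxy for delivery, but the plan does not label it as one.

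**Conclusion.** The point holds as a limited defect of definition. I1 and the logic model place fidelity on the side of what was offered; Protocol section 9.1 and the SAP measure receipt among enrolled fathers against 100%. The result cannot separate non-delivery from non-uptake or lack of need, the workshop item does not show whether 40 hours were held, and the benchmark conflicts with the hypothesis and the needs assessment.

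The size cannot be computed, because the documents give no data on offers, need or sessions held. The 54–95% range rests on assumed need and uptake and only shows that a sizeable gap from 100% is compatible with complete offering. It would go too far to say that I1 is formally failed or passed in error. This is a desirable clarification to an implementation question; R1–R3 are unaffected.

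**What to change.** - For I1, report primary workshop hours held per series against the intended 40 hours, from program session records. The plan already tracks program activities in nFORM (Protocol section 5) and intends to use the timing and length of sessions (SAP, dosage analysis), so this should be mainly a different tabulation.
- Keep the four percent-received figures, label them as uptake, and read them alongside I2.
- Reconcile the hypothesis in Protocol section 4 (services according to need) with the SAP statement that all participants are to receive all four components, and align Protocol sections 1.1, 3 and 9.1 with the result.
- Where need is recorded at enrollment, also report employment supports and referrals among fathers with that need. Where it is not, keep receipt as a labelled proxy for delivery.

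The cost is a change of SAP wording and a small amount of extra tabulation, with no new survey. The drawback is that the need-based figure may not be available for every service, since the documents do not show how need is coded.
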